1

2

3

4

5     **Title: Randomized Controlled Trial Comparing Clinical and Radiological Outcomes**  
6       **Between C3 Laminectomy with C4-C6 Laminoplasty and C3-C6 Laminoplasty**

7

8       **Study protocol (date: 2017-01-05)**

9

1 **Background**

2 C3 laminectomy in cervical laminoplasty is a modified laminoplasty technique that can  
3 preserve semispinalis cervicis muscle attached to the C2 spinous process. Several previous  
4 studies have shown that this technique can lead to better outcomes of postoperative axial neck  
5 pain and C2-C3 range of motion (ROM) than conventional cervical laminoplasty. However,  
6 there is still a lack of understanding of total and proportional postoperative cervical sagittal  
7 alignment outcomes.

8

9 **Study design**

10 A randomized clinical trial will be conducted on patients with cervical laminoplasty for  
11 treating CSM or OPLL at a single tertiary referral university hospital. Patients will be  
12 randomly assigned to either the LN group (C4-6 laminoplasty with C3 laminectomy) or the  
13 LP group (C3-6 laminoplasty) at a 1:1 ratio. The sample size will be calculated to achieve a  
14 target of 80% power with a two-tailed significance level of 0.05, with a medium effect size  
15 (Cohen's  $d = 0.50$ ), resulting in 63 patients per each group. The trial will enrolled consecutive  
16 patients who underwent cervical laminoplasty from March 2017. Participants' ages will  
17 ranged from 20 to 80 years. Patients with metastatic tumors, combined fractures, or previous  
18 posterior cervical surgeries will be excluded from this study. Patients with a diagnosis of  
19 CSM or OPLL will be assessed prior to randomization by a neurosurgical specialist through a  
20 combination of history-taking, clinical examination, and radiological workup, including  
21 dynamic radiographs and cervical spine computer tomography (CT) or magnetic resonance  
22 image (MRI) scans. Diagnosis of CSM will be based on symptoms of myelopathy and  
23 stenosis at two or more cervical levels on MRI. Diagnosis of OPLL will be made based on  
24 CT findings. The randomization process, surgical group options, and required follow-up  
25 evaluations and imaging will be fully explained to eligible patients by a neurosurgical

1 specialist. After obtaining informed consent, patients will be randomized using a computer-  
2 generated block design in 1:1 ratio with concealed assignment managed by an independent  
3 research nurse. The attending surgeons, patients, and staff members in the operating room  
4 will be blinded to the surgical method until the day of surgery. A concealed paper indicating  
5 the patient's assigned group will be provided in the operating room, and the surgeon will  
6 verify the patient's group just before commencing the surgery. This study was approved by  
7 the hospital's Institutional Review Board (IRB number: H-1610-136-804).

8

9 **Data collection and outcomes**

10 Data will be collected using patient-reported outcome questionnaires and plain x-rays taken at  
11 the outpatient clinic before surgery and at 1, 2, and 3 years postoperatively. Patients will  
12 record their outcomes directly without assistance of the surgeon or other study participants.  
13 Radiological parameters will be assessed using 150% magnified images by one of the authors  
14 (a fellow). Three measurements will be performed, and the median value will be selected as  
15 the final measurement. The measurements will be conducted utilizing the measuring tools  
16 within the institution's Picture Archiving and Communication System (M6, Infinit  
17 Healthcare, Seoul, Korea) operating on a Microsoft Windows environment (Microsoft Corp.,  
18 Redmond, WA, USA). We selected C2-C7 Cobb angle (C2-C7 CA) as the primary outcome  
19 measure, considering the importance of postoperative kyphotic changes in cervical  
20 laminoplasty, which have been associated with long-term recurrent myelopathy and chronic  
21 neck pain. Additionally, we chose the Neck Disability Index (NDI) as another primary  
22 outcome measure to evaluate axial neck pain, as it is commonly acknowledged as a potential  
23 advantage of C3 laminectomy. Secondary outcome measures included other radiologic  
24 parameters such as C2-C3 Cobb angle (C2-C3 CA), C4-C7 Cobb angle (C4-C7 CA), cervical  
25 sagittal vertical axis (cSVA), T1 slope (T1S) and T1 slope minus cervical lordosis (T1S-CL),

1 as well as presence of C2-C3 interlaminar fusion. Other clinical outcomes, such as numerical  
2 rating scores for neck (NRS-N) and limb (NRS-L) and the Euro-Quality of Life-5 Dimension  
3 (EQ-5D), will be also assessed. We will examine operation-related factors, including open  
4 side, presence of dome-like laminectomy at the C2 or C7 level, operative time, estimated  
5 blood loss, and complications such as hinge fracture, neural injury, dural injury, and wound  
6 infection.

7

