## 8 **Statistical analysis plan**

9 Outcomes will be analyzed using the modified intention-to-treat (mITT) strategy. The mITT  
10 population will consist of all participants with randomly assigned surgery and have available  
11 at least a year of postoperative data from 1 to 3 years. Baseline and operation-related  
12 characteristics of the LN and LP groups will be compared using independent t-tests for  
13 continuous variables, and chi-square tests or Fisher's exact tests for categorical variables.  
14 Postoperative clinical outcomes and radiological parameters will be compared between  
15 groups and over time using linear mixed-effects models, with fixed effects including  
16 preoperative values of tested variables, group, time, interaction between group and time,  
17 other factors with possible relation with outcomes such as age, BMI and disease, and a  
18 random effect of subjects. Least squares mean for postoperative clinical outcomes and  
19 radiological parameters will be estimated. Comparisons will be made between the treatment  
20 groups. For variables with a significant difference in the interaction between time and group,  
21 post-hoc analysis will be performed for each time point and adjusted p-values will be  
22 evaluated using the Bonferroni method. All data will be analyzed using SPSS software  
23 version 27.0 (SPSS, Chicago, IL, USA), with statistical significance defined at  $p < 0.05$  (two-  
24 sided).

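### Does the 80% power at 63 per group fail because no visit or contrast is named and the visit tests sit behind an interaction gate?

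*Combined protocol and SAP*

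**What the plan says.** The Study design section of the combined protocol and SAP states a "target of 80% power with a two-tailed significance level of 0.05, with a medium effect size" (Cohen's d of 0.50) and 1:1 allocation, "resulting in 63 patients per each group". It attaches no outcome, visit, model contrast or loss allowance to that figure.

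The Data collection and outcomes section names two primary outcomes, C2-C7 Cobb angle and NDI, collected at "the outpatient clinic before surgery and at 1, 2, and 3 years postoperatively". No primary visit is named. The reason given for the Cobb angle is kyphotic change after "laminoplasty, which have been associated with long-term recurrent myelopathy and chronic" neck pain.

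The Statistical analysis plan compares outcomes between "groups and over time using linear mixed-effects models, with fixed effects including" the preoperative value, group, time and their interaction, with a random subject effect. It estimates least squares means and compares the treatment groups. It then adds a conditional step: "For variables with a significant difference in the interaction between time and group", "post-hoc analysis will be performed for each time point and adjusted p-values will be" obtained by the Bonferroni method. The analysis set takes randomized patients with "at least a year of postoperative data from 1 to 3 years".

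**The concern.** The sample size rests on one unadjusted two-group comparison, and the analysis plan contains no test of exactly that form. It has an overall group comparison across three annual visits, and visit-specific tests that must pass an interaction gate and then a stricter threshold.

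If the difference between techniques were small at year 1 and reached d = 0.50 only at year 3, the overall comparison would be diluted. The year-3 test would pay for both the gate and the Bonferroni adjustment. A real late difference could then be missed, although a single pre-named year-3 contrast from the same model would have found it. If the two routes disagreed, readers might also dispute which one answers the primary question. Three years of follow-up with no stated loss allowance adds to the doubt.

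**Working it through.** **Inputs.** From the documents: d = 0.50, two-sided alpha 0.05, 80% power, 63 per group, three annual visits, baseline-adjusted random-intercept model. Assumed, because the documents give no values: baseline-to-follow-up correlation r, between-visit correlation rho, shape of the effect over time, Bonferroni divisor of 3, and loss. All figures are per primary outcome at 0.05. Variance explained by age, BMI and disease is ignored; it would raise every figure.

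**1. The plan's own figure.** n = 2 × (1.960 + 0.8416)² / 0.5² = 62.79, rounded up to 63. Power at 63 is 80.1% by the normal approximation and 79.5% by the noncentral t. The figure reproduces.

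**2. Constant d = 0.50, overall group comparison.** The adjusted three-visit mean has variance v = (1 + 2 rho)/3 − r², so the effective effect is 0.5/√v. For r = 0 and rho = 0.9, v = 2.8/3 = 0.933 and the effect is 0.518.

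| r | rho | 63 per group | 57 (10% lost) | 50 (20% lost) |
|---|---|---|---|---|
| 0 | 0.9 | 82.2% | 78.2% | 72.7% |
| 0.3 | 0.9 | 85.8% | 82.2% | 76.9% |
| 0.5 | 0.9 | 92.0% | 89.3% | 85.0% |
| 0.5 | 0.7 | 96.4% | 94.6% | 91.6% |

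With complete data every cell exceeds 80%. The loss columns remove lost patients entirely. That is pessimistic, because the plan keeps anyone with one postoperative year and the mixed model uses partial follow-up.

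**3. Linear build-up (1/6, 1/3, 1/2 SD at years 1, 2, 3).** Success means a significant overall effect, or a significant interaction followed by a year-3 test at 0.05/3. Simulated power at 63 per group, complete data:

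| r | rho | Power |
|---|---|---|
| 0 | 0.7 | about 66% |
| 0 | 0.9 | about 65% |
| 0.3 | 0.7 | about 71% |
| 0.3 | 0.9 | about 70% |
| 0.5 | 0.7 | about 81% |
| 0.5 | 0.9 | about 79% |
| 0 | 0.5 | about 70% |
| 0.5 | 0.5 | about 86% |
| 0.7 | 0.7 | about 95% |
| 0.7 | 0.9 | about 93% |

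The shortfall is largest where the preoperative value says little about follow-up while the follow-up visits agree closely with each other. Where the two correlations are equal, at 0.5 or 0.7, it disappears even under the build-up.

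**4. Error rate.** With no true difference, the overall-or-gated-year-3 rule rejects in 5.1 to 5.6% of simulated trials, so the second route hardly inflates the error.

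**5. What a named year-3 contrast would buy.** Its effective effect is 0.5/√(1 − r²). Power at 63 is 79.5% for r = 0, 83.1% for r = 0.3 and 89.5% for r = 0.5.

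- Under the build-up at r = 0, rho = 0.7, the gain is 79.5 − 66.1 = 13.4 points.
- Under a constant effect at r = 0, rho = 0.5, v = 2/3 and the overall comparison has 92.7%, so testing year 3 alone gives up about 13 points.

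Which choice is better depends on a trajectory that the documents do not state.

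**The case for a change.** The strongest case for a change is that a power statement should be tied to the test that will be run, and this one is not. The omission is real: no outcome, visit, contrast or retention accompanies d = 0.50, and neither redaction nor text extraction explains it. The scenario figures also reproduce under their assumptions, and the remedy would be two sentences. That the answer moves so much with unstated choices can itself be called a defect. Loss matters too: with no help from the baseline value, whole-patient loss of 10% or 20% takes the single unadjusted comparison to 75.4% or 69.7%.

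What stands is the request for clearer reporting. The claim of a power deficit does not stand, for three reasons.

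- The passage cited for a late effect describes late consequences of kyphosis. It does not say that the difference between the techniques grows from year 1 to year 3. The reason given for NDI, axial neck pain, mentions no late effect. A group-by-time term is routine and implies no particular shape.
- The plan is not silent on order. It compares the groups from the model and labels the visit tests post hoc and conditional. The natural reading puts the overall comparison first.
- The plan does not state the Bonferroni divisor of 3.

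**Conclusion.** No change to the plan is needed. The figure of 63 per group is correct for the calculation described. With complete data and a sustained d = 0.50, the planned overall comparison has 82% power or more for rho up to 0.9. Power of about 65 to 81% belongs to one assumed scenario (linear build-up, rho 0.7 to 0.9, r from 0 to 0.5, three-way Bonferroni) and is not a property of the plan.

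What remains is missing detail that an analyst would fill sensibly by taking the model's overall group comparison as the lead result and the visit tests as follow-up. Choosing year 3 over the three-visit average is a trade-off worth up to about 13 points in either direction, and the documents give no basis for preferring one.

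The conclusion on loss is weaker. If whole patients are lost and the baseline value carries no information, power for a constant effect at rho = 0.9 falls to 78.2% at 10% loss and 72.7% at 20%. At r = 0.5 it stays at 85.0% or above. Whether the two primary outcomes should share the 0.05 is a separate question that these figures do not address.

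### Patient blinding is stated only up to the day of surgery, before every postoperative NDI, a self-reported primary outcome

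*Combined protocol and SAP*

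**What the plan says.** The Study design section gives one blinding rule for three parties: "The attending surgeons, patients, and staff members in the operating room" "will be blinded to the surgical method until the day of surgery". It then describes a concealed paper in the operating room, from which the surgeon verifies the patient's "group just before commencing the surgery". Earlier in the same section, the matters to be explained to eligible patients before consent begin: "The randomization process, surgical group options, and required follow-up".

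The Data collection and outcomes section schedules questionnaires and plain x-rays at the outpatient clinic before surgery and 1, 2 and 3 years after it. It names the C2-C7 Cobb angle as a primary outcome and continues: "Additionally, we chose the Neck Disability Index (NDI) as another primary" "outcome measure to evaluate axial neck pain, as it is commonly acknowledged as a potential" advantage of C3 laminectomy. On how questionnaires are completed, it says that patients "record their outcomes directly without assistance of the surgeon or other study participants".

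The Statistical analysis plan adjusts for the preoperative value of each outcome. It contains no check of blinding and no related sensitivity analysis.

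**The concern.** For NDI the patient is the assessor, so what the patient knows about the operation is part of the measurement. A blinding rule that stops on the day of surgery covers the preoperative questionnaire and none of the postoperative ones. If some patients learn their group and hold an expectation about it, mean NDI can differ between arms without any true effect. The same applies to the secondary patient-reported outcomes (the neck and limb pain scores and EQ-5D).

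The plan's own rationale suggests a direction. It regards less neck pain as a possible advantage of C3 laminectomy, so expectation would more plausibly favour the C3 laminectomy (LN) arm. That is an inference from the investigators' reasoning, not evidence of what patients believe.

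**Working it through.** **Side-by-side reading**

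| Party | Blinding stated to end | Reason given | Status at years 1, 2 and 3 |
|---|---|---|---|
| Surgeon | day of surgery | must verify the group in order to operate | knows the group |
| Operating-room staff | day of surgery | none separately stated; present at the operation | not relevant to NDI |
| Patient | day of surgery | none | not stated |

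The single cut-off fits the first two rows. For patients, no reason is given and nothing replaces the rule afterwards.

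**Do the existing provisions close the gap?**

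- Self-completion keeps the surgeon and others from influencing the answers as the form is filled in. It does not affect what the patient already knows.
- Adjustment for the preoperative value removes chance baseline differences. A reporting shift that arises after surgery is not in the baseline value, so it stays in the group effect.
- X-rays are taken at the same visits as the questionnaires. Discussion of the images is therefore a possible route of disclosure, and the text sets no order for the two.

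**The plan's own figure.** The sample size reproduces. With d = 0.50, two-sided 0.05 and 80% power, the normal approximation gives 2 × (1.960 + 0.842)² / 0.50² = 62.8, so 63 per group. The blinding point does not depend on it.

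**Illustration of size (assumed shifts).** The documents give no bias size, no correlations and no share of patients who learn their group. Assume no true effect and a constant difference d, in SD units, in mean reported NDI.

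*Two-sample t-test:* noncentrality = d × √(63/2) = 5.612 d, with 124 degrees of freedom.

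| d | noncentrality | P(p < 0.05) |
|---|---|---|
| 0 | 0 | 5.0% |
| 0.1 | 0.561 | 8.6% |
| 0.2 | 1.122 | 20.0% |
| 0.3 | 1.684 | 38.6% |

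*Average of three visits with baseline as covariate:* the residual variance is (1 + 2r)/3 − b², where r is the correlation between postoperative visits and b the baseline-to-postoperative correlation. Noncentrality = 5.612 d / √variance, with 123 degrees of freedom.

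| r, b | variance | d = 0.1 | d = 0.2 | d = 0.3 |
|---|---|---|---|---|
| 0.9, 0.2 | 0.893 | 9.1% | 21.8% | 42.4% |
| 0.8, 0.3 | 0.777 | 9.7% | 24.4% | 47.4% |
| 0.7, 0.3 | 0.710 | 10.1% | 26.2% | 50.9% |
| 0.5, 0.5 | 0.417 | 13.9% | 40.7% | 73.5% |

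The last row stands well apart from the others and should not be read as typical.

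*Half of each arm learns the group:* the mean shifts halve to 0.05, 0.10 and 0.15, and the t-test figures fall to 5.9%, 8.6% and 13.3%.

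These tables show how a shift would pass into the test. They say nothing about whether a shift will occur in this trial. They also hold the shift constant over three years; a shift that fades was not examined.

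**The case against.** The strongest reply is that this is a silence and not a demonstrated fault. Only the surgeon's unmasking is described, and no visible step discloses the group to patients. What patients are told after surgery might stand in consent material, which is not available here. Both arms receive C4-C6 laminoplasty and differ only in how C3 is treated, so a patient would probably have to be told, or shown images, to know the arm. Bias then needs two unverified steps: patients learn their group, and they hold a directional expectation. The size figures are wholly assumed and would be the same for any self-reported outcome with 63 per group.

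Much of this stands. A reader might infer that patients will be told their group, that they are told one operation is better, or that the NDI comparison is already biased. The documents support none of these. Explaining the surgical options tells patients that two procedures are compared, not that one is superior. Nor does the point reach the whole trial: the Cobb angle is measured on radiographs and is not open to this mechanism.

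What does not stand is the suggestion that the text is merely silent. It states a rule with an end point for patients, and that end point comes before every postoperative questionnaire. The similarity of the arms also cuts the other way: if patients cannot easily tell which operation they had, keeping them blinded is realistic.

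A fair objection to the remedy is that asking patients every year whether they know their group could prompt them to find out before the next NDI. The fix therefore asks only once.

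**Conclusion.** The point holds in a limited form. Followed as written, the plan's protection of patients ends before every postoperative NDI, and their status at years 1, 2 and 3 is unspecified. Self-completion and baseline adjustment do not make up for this. The exposure covers NDI, the two pain scores and EQ-5D, but not the C2-C7 Cobb angle.

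The size of any bias is unknown from the documents; it is nil if no patient learns the group or if knowing it does not change the answers. The priority of the point rests on the blinding rule and the low cost of changing it, not on the illustrative percentages. It is a worthwhile improvement, held with medium confidence because the consent material cannot be seen.

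**What to change.** Amend the blinding sentence so that surgeons and operating-room staff learn the group on the day of surgery, while patients stay blinded until their 3-year questionnaire is complete. Allow disclosure on clinical need or at the patient's request, and record it when it happens.

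At each visit, have the questionnaire completed before images are discussed, and instruct clinic staff not to volunteer the group. After the final questionnaire, ask each patient once whether and when they learned their group, and report the counts by arm.

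If patient blinding cannot be kept, state that NDI is an unblinded outcome and interpret it with that limitation.

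**Cost:** one amended sentence, matching consent wording, an instruction to clinic staff, and one question at an existing visit (at most 2 × 63 = 126 answers). No extra patients, visits or assessors are needed. The downsides are that staff must avoid casual disclosure for three years, that some patients will still learn their group, and that a single question at the end relies on recall and misses patients who do not reach the 3-year visit.

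### The plan describes no masking of the single author-reader who measures the co-primary C2-C7 Cobb angle, so a systematic reading difference between arms is possible

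*Combined protocol and SAP*

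**What the plan says.** Under Data collection and outcomes, the plan names two primary outcomes. The first is radiological: "We selected C2-C7 Cobb angle (C2-C7 CA) as the primary outcome" measure. The second is a questionnaire: "Additionally, we chose the Neck Disability Index (NDI) as another primary" outcome. Patients complete the questionnaires themselves.

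The same section assigns the film readings to one person: "Radiological parameters will be assessed using 150% magnified images by one of the authors", identified as a fellow, using the measuring tools of the hospital's picture archive (PACS). On repeat readings it says "Three measurements will be performed, and the median value will be selected as" the final value. Plain films are taken before surgery and at 1, 2 and 3 years. The reading list also includes the C2-C3 and C4-C7 Cobb angles, cSVA, T1 slope, T1 slope minus cervical lordosis, and C2-C3 interlaminar fusion.

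Blinding is described once, at the end of Study design. It covers "The attending surgeons, patients, and staff members in the operating room", who "will be blinded to the surgical method until the day of surgery". No image reader or outcome assessor is named there. The plan mentions no coding of films, random reading order, covering of anatomy, second reader or agreement check.

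**The concern.** The arms differ in whether the C3 lamina is removed (LN) or kept (LP). A film taken a year or more later may therefore disclose the arm to whoever measures it, even if that person never sees the allocation list. Looking for C2-C3 interlaminar fusion draws the eye to the same area.

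A Cobb angle is a number, but it depends on lines that a person places on the image. If the reader can tell the arm and places those lines slightly differently in one arm, the difference enters the estimated treatment effect directly. The readings at stake are one of the two primary outcomes and all the radiological secondary outcomes.

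**Working it through.** **1. Does the stated blinding reach the reader?** The blinded groups are surgeons, patients and operating-room staff, and their blinding stops on the day of surgery. The first postoperative film is planned at 1 year. So the stated blinding neither names the reader nor lasts into the period when the outcome films are read.

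**2. Does the median of three protect against a lean?** Write each reading as true angle + arm-specific shift *b* + random error. The median of three readings by the same person is centred on true angle + *b* (for symmetric error). Random error shrinks and *b* stays.

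**3. Does baseline adjustment protect?** The Statistical analysis plan adjusts for the preoperative value. A preoperative film cannot show which operation will follow, so a shift that arises only after surgery is not in the baseline value and is not adjusted away.

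**4. The plan's own figure.** Inputs from Study design: d = 0.50, two-sided alpha 0.05, 80% power, 1:1 allocation.
- Normal approximation: n = 2(1.960 + 0.842)² / 0.50² = 62.8, so 63 per group. This reproduces the stated 63.
- Exact t-test: 63.8, so 64 per group; power at 63 is 79.5%. The difference is immaterial here.

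**5. Illustration of a lean.** Assumptions: no true difference, 63 per group, one two-sample t-test, and a consistent between-arm reading shift of *b* SD. Degrees of freedom = 2 × 63 − 2 = 124; critical value 1.979; noncentrality = *b* × √(63/2) = 5.612 *b*. The false-positive rate is the probability that a noncentral t falls outside ±1.979.

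| Assumed lean (SD) | Noncentrality | False-positive rate | Lean as share of d = 0.50 |
|---|---|---|---|
| 0 | 0 | 5.0% | 0% |
| 0.10 | 0.561 | 8.6% | 20% |
| 0.15 | 0.842 | 13.3% | 30% |
| 0.20 | 1.122 | 20.0% | 40% |

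The documents give neither an SD for the Cobb angle nor any size for a reader lean, so the leans are assumed and left in SD units.

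**6. Sensitivity to the planned model.** The plan uses a baseline-adjusted mixed model over three visits, not one t-test. As an approximation, take the mean of three postoperative visits adjusted for baseline, with all pairwise correlations equal to ρ (assumed; none is given). The residual variance is (1 + 2ρ)/3 − ρ².
- ρ = 0.5: variance 0.417, SD 0.645. A lean of 0.10 becomes 0.155 residual SD, giving 14%; a lean of 0.20 becomes 0.310, giving 41%.
- ρ = 0.8: variance 0.227, SD 0.476. A lean of 0.10 becomes 0.210, giving 22%; a lean of 0.20 becomes 0.420, giving 65%.

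A more precise analysis shrinks the standard error but not the lean, so under these assumptions the simple t-test does not exaggerate the effect of a given lean.

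**The case against.** **Silence is not unmasking.** A reader might infer that the films are read unmasked and that the fellow knows the arm. The documents do not say so; they only describe no masking. That the film shows the missing lamina is likewise an inference from the procedures. This stands, and the point is limited accordingly.

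**Not every film can disclose the arm.** Preoperative films cannot show it anatomically. This stands; the exposure is confined to the postoperative films.

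**No directional expectation is stated for this outcome.** Background reports earlier evidence of benefit for axial neck pain and C2-C3 motion, and describes sagittal alignment as poorly understood. The C2-C7 angle is also numeric, and its end levels are not the level at which the arms differ. A reader might infer that the measurement will favour C3 laminectomy; the documents do not support that. The direction is unknown and the lean may be small. But an unknown direction also means no analysis can correct for it in advance.

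**The lean sizes are hypothetical.** This stands. The percentages show what a lean would do, not how likely one is, and they are not this trial's error rates.

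**The weakness is recoverable.** It is tempting to say that such a bias could never be detected or removed afterwards. Measurements are made in a picture archive, so provided the films are kept, a masked re-reading could test for a lean and replace the values. This stands and lowers the urgency, but the re-reading has to be specified if it is to happen.

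**Half the primary evidence is untouched.** The Neck Disability Index is recorded by the patient without help from the surgeon. This stands as far as this reader is concerned.

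**Conclusion.** The concern holds in a limited form. As written, the plan describes no masking for the one author who measures the co-primary C2-C7 Cobb angle and the other film measures, and the blinding it does describe ends before any outcome film is taken. A systematic reading difference by arm is therefore possible, and neither the median of three readings nor baseline adjustment would remove it.

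Its direction and size cannot be told from the documents. The illustrative rates of about 9%, 13% and 20%, against a nominal 5%, rest on assumed leans of 0.10, 0.15 and 0.20 SD, no true difference, 63 per group and a single t-test. The documents do not show that bias has occurred, that the reader knew the allocation, or that the Neck Disability Index is affected by this reader. The case for a change is that the safeguard is inexpensive, protects a primary outcome, and can still be applied to archived films.

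**What to change.** Add to Data collection and outcomes:

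- Films are read under a study code, without name or date, in random order across patients and postoperative visits. The independent research nurse already in the plan could prepare them.
- The planned reader has no access to allocation or operative notes while reading.
- For the Cobb angles, cSVA and T1 slope, the C3-C6 posterior elements are covered where feasible, because these measures rely on vertebral bodies and endplates.
- C2-C3 interlaminar fusion, which needs the posterior elements visible, is read afterwards in a separate session.
- Any films already read are re-read in this way from the archive.

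No additional reader or imaging is needed. The work is preparing up to 126 × 3 = 378 postoperative films, or 126 × 4 = 504 with baseline, by existing staff. Coded, covered images also change the reading workflow inside the picture archive. Masking will be imperfect on some films, and unoperated baseline films will identify themselves as such.

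### Two primary outcomes are each tested at an unsplit two-sided 0.05, with no success rule, testing order or named primary contrast

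*Combined protocol and SAP*

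**What the plan says.** Under Data collection and outcomes, the first choice is worded in the singular: "We selected C2-C7 Cobb angle (C2-C7 CA) as the primary outcome". A second follows: "Additionally, we chose the Neck Disability Index (NDI) as another primary" outcome. Each has its own reason: kyphotic change after surgery for the angle, and axial neck pain for NDI. Neither is ranked above the other, and nothing says how the two results combine into a conclusion.

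Study design sizes the trial once, with a "target of 80% power with a two-tailed significance level of 0.05, with a medium effect size" of d = 0.50, giving 63 per group. It names no outcome for this calculation.

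The Statistical analysis plan fits a linear mixed model to each outcome, with fixed effects that include "preoperative values of tested variables, group, time, interaction between group and time". On the test itself it says: "radiological parameters will be estimated. Comparisons will be made between the treatment" groups. After a significant group-by-time interaction, "post-hoc analysis will be performed for each time point and adjusted p-values will be" obtained by Bonferroni. One threshold serves all tests, "with statistical significance defined at" two-sided p < 0.05.

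**The concern.** Two things are left open: how the two primary results combine, and which model result represents each outcome. Both could be settled after the data are seen.

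The Bonferroni step does not close the gap. It works within one variable, across years 1, 2 and 3, and only after that variable's interaction is significant. It places no limit on error across the Cobb angle and NDI together.

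What is at stake depends on the missing rule:

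- **Either outcome suffices:** the false-positive rate for the primary conclusion exceeds 5%.
- **Both are required:** error is controlled, but the stated 80% power is for one test and not for the pair.
- **Two separate questions:** each test keeps its own 5% error, but the report may not then claim success because one of the two was positive, nor make a joint claim.

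**Working it through.** **Inputs from the documents.** Two primary outcomes and three postoperative visits (Data collection and outcomes); two-sided alpha 0.05, 80% power, d = 0.50, 63 per group, 1:1 allocation (Study design); one two-sided 0.05 threshold (Statistical analysis plan). The documents give no correlation between outcomes, between visits, or between baseline and follow-up, so those values are assumed below.

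**1. The plan's own figure.** n per group = 2(1.960 + 0.842)² / 0.50² = 62.8, so 63. This matches. Power at 63 per group is 80.1% by the normal approximation and 79.5% by the t-test. The calculation is therefore for one unadjusted two-group comparison of one outcome.

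**2. Either outcome suffices, one test each.** With independent outcomes the chance of at least one false positive is 1 − 0.95² = 0.0975. For correlated outcomes it is one minus the bivariate normal probability that both statistics lie within ±1.960.

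| Assumed correlation between outcomes | Each tested at 0.05 | Holm |
|---|---|---|
| 0 | 0.0975 | 0.0494 |
| 0.5 | 0.0907 | 0.0465 |
| 0.9 | 0.0704 | 0.0362 |

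The Holm column assumes no effect on either outcome. There, Holm errs only if the smaller p-value is below 0.025.

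**3. Either outcome suffices, with the gated visit tests also counted.** Here an outcome is positive if the group effect has p < 0.05, or if the interaction has p < 0.05 and any visit has p < 0.05/3. A simulation with three complete visits and between-visit correlation 0.2 to 0.6 gives:

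- 12.7% to 11.0% at between-outcome correlation 0
- 11.9% to 10.3% at 0.5
- 9.3% to 8.0% at 0.9

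That is about 8-13%. The range moves with the assumptions: no between-visit correlation and independent outcomes give 13.7%, and 0.9 for both correlations gives 7.2%.

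**4. Both required.** On the plan's t-test basis with independent outcomes, joint power is 0.7952² = 0.632. It rises to 0.68 at correlation 0.5 and 0.74 at 0.9.

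**5. Power cost of Holm on the plan's own basis.** Power is 0.7952 at alpha 0.05 and 0.7041 at 0.025, a difference of 0.0910 before rounding. Under Holm an outcome is significant if its p is below 0.025, or if its p lies between 0.025 and 0.05 and the other p is below 0.025. For independent outcomes:

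- both effects real: 0.7041 + 0.0910 × 0.7041 = 0.768
- other outcome null: 0.7041 + 0.0910 × 0.025 = 0.706

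**6. Power under the planned model.** Suppose d = 0.50 is in raw single-visit SD units, all visits are complete, and the contrast is the baseline-adjusted three-visit average. The variance factor is (1 + 2w)/3 − b², with w the visit-to-visit and b the baseline-to-visit correlation.

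- w = b = 1/3: factor 0.444, effective d = 0.75, per-outcome power 98.7%.
- w = 0.7, b = 0.3: factor 0.71, per-outcome power 91.1%, joint 82.9%, Holm 90.2% (both real) or 85.6% (other null).

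Missing visits would lower these figures, and the analysis set admits participants without all three visits. The documents do not say which scale d is on.

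**The case against.** The strongest reply is that the inflation is hypothetical. No passage proposes an either-one claim. Each outcome has its own rationale, and the trial's title speaks of clinical and radiological outcomes. Read as one radiological and one clinical question, each test keeps 5% error and needs no adjustment. This reading is legitimate, but the plan does not state it, and it rules out neither of the alternatives. What stands is that 7-10% is a conditional figure, not the demonstrated error rate of the trial.

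A second reply is that the visit tests are labelled post-hoc and gated by the interaction, which suggests that the overall group comparison is the main test. This largely stands. A reader might infer from the open wording that the plan's error rate is 8-13%. The documents do not support that: they nowhere make the visit tests a route to primary success, and the figure also assumes complete visits and a chosen range of correlations. It is a sensitivity figure only. It remains true that no contrast is labelled primary.

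A third reply is that the mixed model is more powerful than the t-test used for sizing, so joint power may be adequate. It may be. But a reader who infers from favourable correlations that power is at least 97% or so goes beyond the documents: that floor needs complete data and equal baseline-to-visit and visit-to-visit correlation, and a different pair of values gives 82.9% joint. Nor does the 63% show that the trial is underpowered, since it holds only on the sizing basis.

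Finally, a correlation of 0.9 between a radiographic angle and a disability score has no basis in the documents. It serves as a favourable bound, and even there the either-one error exceeds 5%.

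**Conclusion.** The gap is real and should be fixed. The plan has two unranked primary outcomes, one unsplit threshold, no success rule and no named contrast, and nothing in it controls error across the pair.

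The size is conditional on the rule adopted. An either-one claim carries a 7-10% chance of a false-positive primary with one test per outcome, and 9.1% to 9.75% for correlations between 0 and 0.5. Requiring both keeps error at or below 5%. Declaring two separate questions also resolves the error issue, provided that no joint or either-one claim follows.

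The one-test error figures rest on normal test statistics and assumed correlations between outcomes. The power figures on the sizing basis take d = 0.50 as true for each outcome in an unadjusted comparison of 63 per group.

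**What to change.** In the Statistical analysis plan, name one primary contrast per outcome. One option is the model-based LN-LP difference averaged over years 1 to 3. Label the interaction and the per-visit comparisons as secondary. Then add a sentence such as: *The two primary tests form one family at two-sided alpha 0.05 and are tested by Holm: the smaller p-value against 0.025 and, if that is significant, the other against 0.05.*

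If both outcomes are meant to be required, say so and restate the power for the chosen contrast; no alpha split is then needed. If they are meant as two separate questions, say so and make no joint or either-one claim.

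The change is a few sentences and needs no new data. Adopting Holm at the planned size lowers per-outcome power, on the plan's own basis, from 79.5% to 76.8% if both effects are real and independent, or to 70.6% if the other outcome has no effect. Under the adjusted mixed model the loss depends on correlations and missing visits that the documents do not give, so no minimum power should be claimed.
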